5.2.2. Screening

The research participants will be screened following the inclusion and exclusion criteria.

5.2.3. Inclusion Criteria

- Age ≥18 years, regardless of gender;
- Patients hospitalized in moderate to severe stages in line with the Ministry of Health classification⁹;
- Positive diagnostic test for SARS-CoV-2 by molecular amplification of the virus RT-PCR diagnosed from respiratory specimen (nasopharyngeal, oropharyngeal, lower respiratory tract [e.g., sputum) collected <96 hours before randomization;

⁹The Brazilian Ministry of Health classifies the symptoms of COVID-19 into:

Mild: Flu-like symptoms (cough, sore throat, or runny nose), followed or not by: anosmia (olfactory dysfunction), ageusia (taste dysfunction), runny nose, diarrhea, abdominal pain, fever, chills, myalgia, fatigue, headache;

Moderate: Persistent cough + daily persistent fever or persistent cough + progressive worsening of another symptom related to COVID-19 (adynamia, prostration, hyporexia, diarrhea) or at least one of the above symptoms + presence of risk factor.

Severe: Severe acute respiratory syndrome: influenza syndrome presenting with dyspnea/respiratory distress or persistent chest pressure or $_{02}$ saturation (SpO2) less than 95% on room air or Bluish coloration of lips or face.

- Time between symptom onset and inclusion ≤14 days;
- Hospitalization within 48 hours of study inclusion;
- Availability for follow-up during the study period;
- Voluntary adherence to participate in the study and signing of the Informed Consent Form.

5.2.4. Exclusion Criteria

Individuals with one or more of the following characteristics will not be eligible to participate in this study:

- Patients known or suspected to be sensitive to AZVUDINE or excipients (inactive ingredients: microcrystalline cellulose, lactose hydrate, polyvinylpyrrolidone K30, croscarmellose sodium, magnesium stearate);
- Patients diagnosed with pneumonia caused by other pathogens;
- Patients with liver disease (total bilirubin ≥2mg/dL, ALT/TGP and AST/TGO ≥5 times above normal limit); ¹⁰
- Total neutrophil count <750 cells/L;
- Patients with renal insufficiency (glomerular filtration rate ≤60mL/min/1.73m2) or are receiving continuous renal replacement therapy, hemodialysis, or peritoneal dialysis;
- Patients with congestive heart failure (NYHA grade 3/4), untreated symptomatic arrhythmias, or myocardial infarction within 6 months;

HRH.org 華 人 □

AZVUDINE Clinical Trial Design

- Patients with a history of known liver disease (cirrhosis with ChildPugh classification B and C);
- Individuals with malabsorption syndrome, or other conditions that affect gastrointestinal absorption, and circumstances in which patients need intravenous nutrition, or cannot take medications orally or nasogastrically;
- Women who are pregnant or lactating, or of childbearing potential during the study period and within 6 months after termination of administration;
- Patients already included in other clinical trials;
- Patient under treatment for HIV, Hepatitis C, active Hepatitis B;
- Patients being treated with other antivirals (e.g. lopinavir/ritronavir, remdesivir, umifenovir/arbidol, favipiravir, interferon-α);
- Patients being treated with monoclonal antibodies (e.g. tocilizumab and sarilumab/kevzara);
- Patients who are on a clinical treatment plan that includes concomitant
 administration of any other experimental treatment or off-label use of
 already marketed drugs (e.g. hydroxychloroguine sulfate);
- Patients requiring invasive mechanical ventilation or extracorporeal membrane oxygenation (ECMO) at the time of randomization;
- Any clinically significant medical condition or medical history that, in the investigator's opinion, may discourage participation in the study, such as corrected QT interval >480 on the electrocardiogram, among other conditions.

5.3. VIROLOGICAL DIAGNOSIS

¹⁰ Normal values: BT up to 1.2mg/dL; TGO Adult 12 to 46U/L; TGP Adult 03 to 50U/L; GGT Man 10 to 50U/L, Woman 07 to 32U/L (Instituto Hermes Pardini).

5.3.1. Diagnostic criteria for SARS- CoV-2 infection

The criteria for diagnosis will be based on the World Health Organization Guide, where confirmed cases of SARS-CoV-2 infection will be those performed by molecular testing with viral sequencing by QUALITATIVE real-time PCR /RT-PCR (WHO, 2020a) of nasopharyngeal and oropharyngeal *swab* specimens, bronchoalveolar lavage, nasopharyngeal tracheal aspirate, blood, serum and tissue from lung biopsies.

5.3.2. Process standardization at proof of concept

According to the protocol of the IGZ-1 study, RT-PCR tests will be done every 48h, and since we will probably have patient intake on odd and even days, processing should be done every day, with results every 24h.

Therefore, the ready availability of RT-PCR test results impacts the assessment of eligibility, total treatment time, and early termination of the participant's treatment.

We know that RT-PCR can demonstrate the negative conversion of the presence of virus copies (QUALITATIVE analysis), while a ddPCR can determine the number of virus copies (QUANTITATIVE analysis). However, due to the cost and unavailability of this equipment with ANVISA registration, the analysis must pass through validation, being infrequent in Brazil.

We also know that it is possible to calculate the amount of viral RNA copies by means of a standard curve to quantitatively determine the viral load of an unknown sample from samples with known amounts.

Wang et al, J Clin Invest. 2020 demonstrated that the CT values observed in respiratory samples from critically ill patients were lower (18-22) than those observed in mild patients (32-38). Therefore, the lower the CT, the higher the amount of viral RNA in the sample and consequently the higher the viral load of the volunteer.

From these variables, we standardized the process to quantify the viral load as described below, since **very few studies relate the number of cycles with viral load, or** with the efficacy of the experimental drug. This is a little explored problem that may

bring to light issues of virus behavior in relation to clinical response, already questioned by the FDA.

According to FDA guidance "COVID-19: Development of Biologic Drugs and Products for Treatment or Prevention - Guidance for Industry; 2020," "... virologic endpoints are not appropriate as primary endpoints in a phase III study because there is no established predictive relationship between the magnitude and timing of viral reductions and the extent of clinical benefit of how a patient feels, functions, or survives."

THE PROBLEM

Each RT-PCR equipment has its own sensitivity, and different RT-PCR reagent kits

have different performances, according to the May 2020 technical note "ANVISA
ACCURACY OF ANVISA REGISTERED DIAGNOSTIC TESTS for COVID-19 for qualitative analyses".

The sensitivity of each RT-PCR equipment and kit used varies in the number of CTs to generate the qualitative result (Positive or negative)¹¹.

So, to extract RELIABLE **QUANTITATIVE** data, both the equipment and the reagent kit must be standardized to avoid discrepancies. However, this is not enough, so a standard curve should provide the correlation between CTs and *viral RNA copy* number.

Therefore, we will use the QuantStudio5 RT-PCR equipment, *Applied Biosystems*, NS: 272525086, ANVISA Reg.: 10358940069, to issue reports for statistical accounting and to assist in the standard curve analysis, via dedicated software¹². We will also use the TaqPathTMCOVID-19 CE-IVD RT-PCR¹³ kit (ANVISA Reg.: 10358940107), which can provide us with the viral load-related CT values (viral RNA copies) as a function of the standard curve constructed with the positive control (TaqPath COVID-19 *Control*), which is SARS-CoV-2 viral RNA at a known concentration of 1 x 104 copies/ μ L. By means of the standard curve, using serial dilutions of the positive control, we can arrive at the

concentration (in number of copies) of the viral RNA present in each sample from the volunteers and participants.

For example, it is common to determine the concentration of proteins in a sample using a colorimetric method, the Bradford assay. Similarly, by performing serial dilutions of the positive control we can establish a standard curve (equation y = ax + b) using the CTs obtained for each point on the concentration curve.

The positive RT-PCR result occurs at CTs ≤37. In this case, when viral RNA is present, the specific probe used for detection of SARS-CoV-2 is broken by DNA polymerase, emitting fluorescence. The higher the viral RNA copy number, the higher the fluorescence and therefore the CT value appears earlier during the reaction.

The lower the copy number of the viral RNA, the lower the fluorescence and, consequently, the CT value appears later. CTs values >37 are considered negative. By establishing a curve of viral RNA concentration (present in the positive control), we will obtain a curve of CTs, from lower values (higher viral RNA copies) to higher values (lower viral RNA copies).

The trials approved for the treatment of COVID19 so far use RT-PCR negative conversion monitoring as the endpoint, while the IGZ-1 assay methodology, in addition to obtaining a positive or negative result for the presence of SARS-CoV-2, can also calculate the number of viral copies in each sample and in a practical way:

- It would be possible to determine the behavior of the viral load after the use of the experimental drug and the placebo;
- It would be possible to relate the different viral loads of the positive result to the clinical improvement over time, individually and overall, in the two groups;
- It would be possible to observe the scale of growth (exponential or logarithmic)

¹¹ KiCqStartTM One-Step Probe RT-qPCR ReadyMixTM. Catalog Number KCQS07, KCQS08, KCQS09. SIGMA-ALDRICH 2019-nCov CDC Probe and Primer Kit for SARS-CoV-2 CERTIFICATE OF ANALYSIS. Catalognumber: KIT-nCoV-PP1-1000. Bioresearch Technologies.

²⁰¹⁹⁻nCoV TaqMan RT-PCR Kit. Catalognumber:TM67100, TM67120. NORGEN BIOTEK COPORATION.

¹² Real-time PCR handbook, 2012. Basis of Real-time PCR, Life Technologies. Inc. CO32085 0812.

 $^{^{13}}$ TaqPathTM COVID-19 CE-IVD RT-PCR Kit INSTRUCTIONS FOR USE. Catalog Number A48067 Publication Number MAN0019215.

and the best time for intervention.

In a positive test, there is a significant range of variability in viral RNA copies that may be related to the clinical condition of the participant, and since viral load monitoring will be done every 48h, an algorithm can be reached to explain why positive people have different outcomes.

5.4. MEASURES TO MINIMIZE STUDY BIAS

5.4.1. Randomization

Research participants, according to eligibility at the time of screening and agreement of the Principal Investigator, will be randomized to one of the two study arms (1:1) by Research-IGZ 1.0 software, generating via the system, random numbers that relate the groups to the volunteers, from the data management plan in **ANNEX 2.**

5.4.2. **Blinding**

A physical report of the blinding will be generated as a security measure and sent to the pharmacist for dispensing the investigational product and to the center coordinator in a sealed envelope. Details about blinding can be found in the Randomization topic in **ANNEX 2.**

5.4.3. Breaking the emergency blinding

EMERGENCY CEGENE BREAKING can be **INDIVIDUAL** or **TOTAL**, via the system through the administrator password of the Research-IGZ 1.0 software.

Breaking the blinding must be justified by the Principal Investigator, and it is certain that any breaking of blinding will generate Logs in the system, which can be seen in the audit analyses. In case of unblinding, the Principal Investigator and the center coordinator will opt for INDIVIDUAL unblinding. Only in recurring SAEs, suspected of being related to the investigational product, will the FULL blinding be broken.

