5.1.4. Research location

The present research project will be conducted at Santa Casa de Misericórdia de Campos, located in Parque Tamandaré, Campos dos Goytacazes - RJ. The research center

was pre-selected by the study sponsor due to the profile of the Northern region of the State of Rio de Janeiro, composed of 8 municipalities, with the city of Campos dos Goytacazes - RJ being the most populous and the destination of patients from the macro region.

[figure not shown]

Figure 5: Macroregion of Norte Fluminense

The research center was qualified by the Study Sponsor in compliance with the standards established by the ICH Guidelines for Good Clinical Practice GCP/ICH - ICH *Topic* E6 (R2) (2016), ANVISA Normative Instruction n^{o.} 20, 2017, which provides for inspection procedures in Good Clinical Practice for Clinical Trials with Investigational Medicines and other applicable regulations.

The choice occurred due to the infrastructure necessary for the flow of the participants' hospitalization and optimization of the logistics of molecular biology analyses. Centralizing the analyses in the SCMC Molecular Biology Laboratory (equipped by the Galzu Institute and certified by ViSa-RJ) and also installing the study's biorepository at the State University of Rio de Janeiro (UENF) were strategic decisions to maintain the quality of the process in the proof of concept (we will explain later).

Renowned national research institutes, such as FIOCRUZ, use the strategy of multicenter models in their studies. However, in studies with the same design profile,

the participating centers are all in metropolitan areas of Rio de Janeiro, most concentrated in the municipality itself. Such a strategy certainly favors the catchment strategy, but it does not bring great contributions to evaluations of the influence of demographic or epidemiologic profiles on the data of the studies. Also, most of these studies involve outpatient follow-up; different from our proposed study, which involves inpatient care and, for this reason, demands a more complex infrastructure to set up a research center.

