5.4.4. Rules for breaking the blinding

This study adopts the double-blind method:

Primary disclosure will be performed after completion of the final version of the statistical plan, audit report and database lock. At this stage, the random numbers will be grouped according to the study arm for statistical analysis by group.

Secondary disclosure discloses the drug corresponding to the group code, experimental drug or PLACEBO. Disclosure documents will be signed by the Sponsor and Research Coordinator.

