12.2. INDEPENDENT DATA AND SECURITY MONITORING COMMITTEE (CIMS)

In order for the trial to meet scientific and ethical standards to the greatest extent possible, ensure the safety and well-being of the participants, as well as the scientific validity and integrity of the data, a CIMS has been established for the trial to review safety and clinical efficacy data, conduct emergency review and assessment of safety-related issues. CIMS members will evaluate adverse events, clinical, statistical, pharmacological and toxicological issues, and if necessary, experts in relevant fields can also be invited to attend the CIMS meeting.

The CIMS will be responsible for evaluating the safety and efficacy of the investigational drug. The CIMS may stop the study for safety.

Throughout the process of this trial, the CIMS will continuously monitor the efficacy and safety data, propose to the principal investigator and sponsor the organization of timely data discussion meeting, analyze the efficacy indicator and safety and will provide suggestions to the Principal Investigator and sponsor for the design of the follow-up trial according to the results of the statistical analysis. This committee will also conduct regular meetings or teleconferences according to the CIMS regulations, and the committee's recommendations include terminating the trial for safety, modifying the protocol, or suspending the trial until more supporting information is available, with the sponsor having priority in the final decision.

The CIMS regulation for working procedures can be found at ANNEX3.

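### Section 5.4.3 answers recurring suspected SAEs with a full code break instead of referral to the monitoring committee, and leaves the trigger and the recipients of the list undefined

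*Protocol*

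**What the plan says.** Section 5.4.3 (Breaking the emergency blinding) provides two levels of break, individual and total, each made "via the system through the administrator password of the Research-IGZ 1.0 software". Three rules follow:

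- On justification: "Breaking the blinding must be justified by the Principal Investigator".
- On the usual level: "the Principal Investigator and the center coordinator will opt for INDIVIDUAL unblinding".
- On the exception: "Only in recurring SAEs, suspected of being related to the investigational product, will the FULL blinding be broken".

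Every break is logged and can be seen at audit. Section 5.4.2 adds that a physical report of the blinding goes to the pharmacist and, in a sealed envelope, to the center coordinator. It refers to Annex 2 for details.

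Section 5.4.4 covers planned disclosure: "Primary disclosure will be performed after completion of the final version of the statistical plan, audit report and database lock".

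Section 12.2 sets up the CIMS, among other things to "conduct emergency review and assessment of safety-related issues". It adds: "The CIMS may stop the study for safety". The committee's working rules are in Annex 3.

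There is one center (section 5.1.4): "The present research project will be conducted at Santa Casa de Misericórdia de Campos".

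**The concern.** The exception is worded as a consequence, not an option: once suspected SAEs recur, the whole code is opened. Three things are left loose.

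- **Trigger.** No count, rate or same-event condition is attached to recurring.
- **Route.** Recurrent suspected drug-related SAEs are the situation for which section 12.2 creates a committee, yet 5.4.3 does not mention it.
- **Aftermath.** Nothing says who may see the full list, or whether enrolment and scoring continue.

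With a single center, a total break covers the whole trial. Section 5.1.2 names blinding of center staff and participants as a protection against bias. The primary endpoint is a fall of at least one WHO category by D15, and the categories in Table 4 turn partly on whether a patient is in hospital and on the type of oxygen support. Those are decisions of the treating team. If that team knew every allocation, later scores, discharges and causality judgements could be influenced by it.

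**Working it through.** The protocol gives no figure on this point, so there is none to reproduce. The check is a comparison of sections, followed by two illustrations.

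**1. Sections side by side**

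| Question | 5.4.3 | 12.2 |
|---|---|---|
| Who assesses recurrent suspected SAEs? | Principal Investigator justifies a break; with the center coordinator, opts for the individual level | CIMS, including in emergencies |
| What follows? | Full blinding is broken | CIMS may stop, or recommend modifying or suspending |
| Who sees allocations? | Not stated | Not stated (Annex 3 not shown) |

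No other section in the document shown, including 9.6 on early stopping and 10.2 on the data system, routes a full break through the CIMS or keeps the list from the site.

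**2. How often might the rule be met?** This is an illustration only.

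Assumptions: recurring means at least two suspected SAEs among the 180 randomised; events are independent; p is the probability per participant. Then

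P(X ≥ 2) = 1 − (1 − p)^180 − 180·p·(1 − p)^179.

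A low anchor for p comes from the protocol. Sections 5.1.2 and 5.1.3 report no SAEs with 262 Hope-4 participants in. The one-sided 95% upper bound for zero events in 262 is 1 − 0.05^(1/262) = 1.14%. If 10% to 30% of SAEs are judged suspected (assumption), p is at most 0.11% to 0.34%.

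Example at p = 1%: 1 − 0.164 − 0.298 = 0.538.

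| p | at least 2 | at least 3 |
|---|---|---|
| 0.11% | 1.8% | 0.1% |
| 0.34% | 12.6% | 2.4% |
| 0.5% | 22.7% | 6.2% |
| 1% | 53.8% | 26.9% |
| 2% | 87.7% | 70.0% |

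The rates of 0.5% and above are assumptions. If recurring means repeats of the same event, the probabilities are lower again.

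**3. What could open scoring do?** This too is an illustration only.

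Assumptions: no drug effect; 50% improve; 81 evaluable per arm (section 11.1); two-sided 5% test; open scoring adds b = 10 points to the drug arm; a share f of participants is scored open. The chance of a significant result in favour of the drug is Φ[(b·f − 1.96·SE0)/SE1], where SE0 and SE1 are the standard errors under the null and under the shifted rates.

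- No bias: 2.5%.
- f = 0.5: the shift is 0.05, SE0 = 0.0785, SE1 = 0.0784. (0.05 − 0.1538)/0.0784 = −1.32, which gives 9.3%.
- f = 1: the shift is 0.10, which gives 24.7%.

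The damage depends on f, that is, on how early the break comes.

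**The case against.** The strongest case against is that several stronger readings go beyond the text. Four are tempting.

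- **That the investigator and coordinator open the full code and the treating team learns every allocation.** The text has these two opting for an individual break. The sentence on the full break is passive and names neither who performs it nor who receives the list. The holder of the administrator password is not stated, and Annex 2 may settle this. Exposure of the site is an inference from the roles named and the single center.
- **That 5.4.3 contradicts 5.4.4.** It does not. Section 5.4.4 governs planned disclosure for analysis, and an emergency exception can stand beside it.
- **That the rule would destroy the primary comparison.** D15 scores recorded before a break stay blinded. A cluster of suspected SAEs might also end the trial under 9.6 or 12.2 before much open scoring took place.
- **That the trigger is likely to be met.** SAE incidences of 5% to 10%, with 10% to 30% suspected, would give 23% to 97% on the two-event reading. Those incidences have no source in the protocol, and the Hope-4 report points lower.

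All four limits stand. In the other direction, Hope-4 patients may have been less ill. Section 8.1 treats an event as an SAE when the investigator cannot decide, and section 8.6 allows a possible relation even where other causes exist. The low anchor is therefore not a forecast either. None of the four limits supplies a definition of recurring, a restriction on recipients or a role for the CIMS.

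**Conclusion.** The point holds as a badly fixed rule. Section 5.4.3 prescribes a full break on an undefined trigger, names only site roles in the decision, and passes over the committee to which the same protocol gives this task.

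The harm is conditional. It arises if the list reaches site staff and the trial continues, and it is confined to participants not yet scored at that time. The size of the risk cannot be estimated from the document. The illustrative probability of at least two suspected SAEs runs from about 2% to 88% as the assumed rate goes from 0.11% to 2%, and it is lower on a stricter reading of recurring. That spread mainly shows how much hangs on an undefined word.

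The section should be changed before it has to be used, because an opened code cannot be closed again.

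**What to change.** - In 5.4.3, limit code breaks at the site to individual participants.
- Replace the full break with immediate referral of recurrent suspected SAEs to the CIMS, and define recurrent. The CIMS reviews data by arm in closed session and recommends continuing, modifying, suspending or stopping.
- State that the investigator, the coordinator and sponsor staff stay blinded until database lock. Since 12.2 gives the sponsor priority in the final decision, the sponsor would act on the recommendation without seeing data by arm.
- Align Annexes 2 and 3, and the handling of the blinding report that 5.4.2 sends to the pharmacist and, sealed, to the center coordinator.

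**Cost.** Rewording of 5.4.3 and related text in 5.4.2 and both annexes, and a short delay while the committee convenes. Section 12.2 already foresees emergency review, but it does not say that the CIMS receives data by arm, so that access must be written into its regulation. Individual emergency breaks remain available throughout.
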